9 COMPUTER SOFTWARE

All analyses will be performed by [REDACTED] using Version 9.4 or higher version of SAS® software. All summary tables and data listings will be prepared utilizing SAS® software.

11 TABLES AND LISTINGS

Programming shells for the tables and listings are provided in a separate document. However, below is a schedule of the tables and listings planned in this SAP. Note that additional tables and listings may be created after this SAP is finalized and therefore will not be listed below (table and listing numbers may change accordingly).

NUMBER	TABLE
14.1.1.1.1	End of Treatment Disposition of Subject by Birth Weight Stratification (2000 - 1501 g, 1500 – 1000 g)\Intent-to-treat Population
14.1.1.1.2	End of Treatment Disposition of Subject by Birth Weight Stratification (999 - 750 g, 749 – 500 g)\Intent-to-treat Population
14.1.1.1.3	End of Treatment Disposition of Subjects Across All Birth Weight Stratifications\Intent-to-treat Population
14.1.1.1.5	End of Study Disposition of Subject by Birth Weight Stratification (2000 - 1501 g, 1500 – 1000 g)\Intent-to-treat Population
14.1.1.1.6	End of Study Disposition of Subject by Birth Weight Stratification (999 - 750 g, 749 – 500 g)\Intent-to-treat Population
14.1.1.1.7	End of Study Disposition of Subjects Across All Birth Weight Stratifications\Intent-to-treat Population
14.1.2.1.1	Maternal Demographic Characteristics by Birth Weight Stratification (2000 - 1501 g, 1500 – 1000 g)\Intent-to-treat Population
14.1.2.1.2	Maternal Demographic Characteristics by Birth Weight Stratification (999 - 750 g, 749 – 500 g)\Intent-to-treat Population
14.1.2.1.3	Maternal Demographic Characteristics Across All Birth Weight Stratifications\Intent-to-treat Population
14.1.2.2.1	Maternal Smoking/Alcohol History by Birth Weight Stratification (2000 - 1501 g, 1500 – 1000 g)\Intent-to-treat Population
14.1.2.2.2	Maternal Smoking/Alcohol/Drug Use History by Birth Weight Stratification (999 - 750 g, 749 – 500 g)\Intent-to-treat Population

14.1.2.2.3	Maternal Smoking/Alcohol/Drug Use History Across All Birth Weight Stratifications\Intent-to-treat Population
14.1.2.3.1	Maternal Reproductive History by Birth Weight Stratification (2000 - 1501 g, 1500 – 1000 g)\Intent-to-treat Population
14.1.2.3.2	Maternal Reproductive History by Birth Weight Stratification (999 - 750 g, 749 – 500 g)\Intent-to-treat Population
14.1.2.3.3	Maternal Reproductive History Across All Birth Weight Stratifications\Intent-to-treat Population
14.1.2.4.1	Maternal Pregnancy/Delivery History by Birth Weight Stratification (2000 - 1501 g, 1500 – 1000 g)\Intent-to-treat Population
14.1.2.4.2	Maternal Pregnancy/Delivery History by Birth Weight Stratification (999 - 750 g, 749 – 500 g)\Intent-to-treat Population
14.1.2.4.3	Maternal Pregnancy/Delivery History Across All Birth Weight Stratifications\Intent-to-treat Population
14.1.3.1	Infant Baseline Characteristics by Birth Weight Stratification (2000 - 1501 g, 1500 – 1000 g)\Intent-to-treat Population
14.1.3.2	Infant Baseline Characteristics by Birth Weight Stratification (999 - 750 g, 749 – 500 g)\Intent-to-treat Population
14.1.3.3	Infant Baseline Characteristics Across All Birth Weight Stratifications\Intent-to-treat Population
14.1.3.5	Infant Baseline Characteristics by Birth Weight Stratification (2000 - 1501 g, 1500 – 1000 g)\Per Protocol Population
14.1.3.6	Infant Baseline Characteristics by Birth Weight Stratification (999 - 750 g, 749 – 500 g)\Per Protocol Population
14.1.3.7	Infant Baseline Characteristics Across All Birth Weight Stratifications\Per Protocol Population
14.1.3.9	Infant Baseline Characteristics by Birth Weight Stratification (2000 - 1501 g, 1500 – 1000 g) and Gestational Age Group (<= 28 Weeks vs > 28 Weeks)\Intent-to-treat Population
14.1.3.10	Infant Baseline Characteristics by Birth Weight Stratification (999 - 750 g, 749 – 500 g) and Gestational Age Group(<= 28 Weeks, > 28 Weeks)\Intent-to-treat Population
14.1.3.11	Infant Baseline Characteristics Across All Birth Weight Stratifications and by Gestational Age Group(<= 28 Weeks, > 28 Weeks)\Intent-to-treat Population

14.1.3.13	Infant Baseline Characteristics by Birth Weight Stratification (2000 - 1501 g, 1500 – 1000 g) and Gestational Age Group (<= 28 Weeks vs > 28 Weeks)\Per Protocol Population
14.1.3.14	Infant Baseline Characteristics by Birth Weight Stratification (2000 - 1501 g, 1500 – 1000 g) and Gestational Age Group (<= 28 Weeks vs > 28 Weeks)\Per Protocol Population
14.1.3.15	Infant Baseline Characteristics by Birth Weight Stratification (999 - 750 g, 749 – 500 g) and Gestational Age Group(<= 28 Weeks, > 28 Weeks)\Per Protocol Population
14.1.4.1.1	Maternal Prior Medications by Drug Class and Preferred Name by Birth Weight Stratification (2000-1501 g,1500–1000 g)\Safety Population
14.1.4.1.2	Maternal Prior Medications by Drug Class and Preferred Name by Birth Weight Stratification (999 - 750 g, 749 – 500 g)\Safety Population
14.1.4.1.3	Maternal Prior Medications by Drug Class and Preferred Name Across All Birth Weight Stratifications\Safety Population
14.1.4.2.1	Maternal Concomitant Medications by Drug Class and Preferred Name by Birth Weight Stratification (2000-1501 g,1500–1000 g)\Safety Population
14.1.4.2.2	Maternal Concomitant Medications by Drug Class and Preferred Name by Birth Weight Stratification (999 - 750 g, 749 – 500 g)\Safety Population
14.1.4.2.3	Maternal Concomitant Medications by Drug Class and Preferred Name Across All Birth Weight Stratifications\Safety Population
14.1.4.3.1	Infant Prior Medications by Drug Class and Preferred Name by Birth Weight Stratification (2000 - 1501 g, 1500 – 1000 g)\Safety Population
14.1.4.3.2	Infant Prior Medications by Drug Class and Preferred Name by Birth Weight Stratification (999 - 750 g, 749 – 500 g)\Safety Population
14.1.4.3.3	Infant Prior Medications by Drug Class and Preferred Name Across All Birth Weight Stratifications\Safety Population
14.1.4.4.1	Infant Concomitant Medications by Drug Class and Preferred Name by Birth Weight Stratification (2000 - 1501 g, 1500 – 1000 g)\Safety Population
14.1.4.4.2	Infant Concomitant Medications by Drug Class and Preferred Name by Birth Weight Stratification (999 - 750 g, 749 – 500 g)\Safety Population
14.1.4.4.3	Infant Concomitant Medications by Drug Class and Preferred Name Across All Birth Weight Stratifications\Safety Population
14.2.2.1	Incidence Rate of NEC by Birth Weight Stratification (2000 - 1501 g, 1500 – 1000

	g)\Intent-to-treat Population
14.2.2.2	Incidence Rate of NEC by Birth Weight Stratification ((999 - 750 g, 749 – 500 g)\Intent-to-treat Population
14.2.2.3	Incidence Rate of NEC Across All Birth Weight Stratifications\Intent-to-treat Population
14.2.2.6	Incidence Rate of NEC by Birth Weight Stratification (2000 - 1501 g, 1500 – 1000 g) and Gestational Age Group(<= 28 Weeks, > 28 Weeks)\Intent-to-treat Population
14.2.2.7	Incidence Rate of NEC by Birth Weight Stratification ((999 - 750 g, 749 – 500 g) and Gestational Age Group(<= 28 Weeks, > 28 Weeks)\Intent-to-treat Population
14.2.2.8	Incidence Rate of NEC Across All Birth Weight Stratifications and Gestational Age Group(<= 28 Weeks, > 28 Weeks)\Intent-to-treat Population
14.2.3.1	Incidence Rate of Sepsis, Feeding Intolerance and Antibiotic Use by Birth Weight Stratification (2000 - 1501 g, 1500 – 1000 g)\Intent-to-treat Population
14.2.3.2	Incidence Rate of Sepsis, Feeding Intolerance and Antibiotic Use by Birth Weight Stratification (999 - 750 g, 749 – 500 g)\Intent-to-treat Population
14.2.3.3	Incidence Rate of Sepsis, Feeding Intolerance and Antibiotic Use Across All Birth Weight Stratifications\Intent-to-treat Population
14.2.4.1	Incidence Rate of Other Complications of Prematurity by Birth Weight Stratification (2000 - 1501 g, 1500 – 1000 g):\Intent-to-Treat Population
14.2.4.2	Incidence Rate of Other Complications of Prematurity by Birth Weight Stratification (999 - 750 g, 749 – 500 g): Study\Part A\Intent-to-Treat Population
14.2.4.3	Incidence Rate of Other Complications of Prematurity Across All Birth Weight Stratifications\Intent-to-Treat Population
14.2.5.1	Hospital Mortality Rate by Birth Weight Stratification (2000 - 1501 g, 1500 – 1000 g)\Intent-to-Treat Population
14.2.5.2	Hospital Mortality Rate by Birth Weight Stratification (999 - 750 g, 749 – 500 g)\Intent-to-Treat Population
14.2.5.3	Hospital Mortality Rate Across All Birth Weight Stratifications\Intent-to-Treat Population
14.3.1.1.1	Exposure to Study Treatment by Birth Weight Stratification (2000 - 1501 g, 1500 – 1000 g)\Safety Population
14.3.1.1.2	Exposure to Study Treatment by Birth Weight Stratification (999 - 750 g, 749 – 500 g)\Safety Population

14.3.1.1.3	Exposure to Study Treatment Across All Birth Weight Stratifications\Safety Population
14.3.1.2.1	Overall TEAEs by Birth Weight Stratification (2000 - 1501 g, 1500 – 1000 g)\Safety Population
14.3.1.2.2	Overall TEAEs by Birth Weight Stratification(999 - 750 g, 749 – 500 g)\Safety Population
14.3.1.2.3	Overall TEAEs Across All Birth Weight Stratifications\Safety Population
14.3.1.2.5	Overall TEAEs by Birth Weight Stratification (2000 - 1501 g, 1500 – 1000 g) and Gestational Age Group (<= 28 Weeks, > 28 Weeks)\Safety Population
14.3.1.2.6	Overall TEAEs by Birth Weight Stratification (999 - 750 g, 749 – 500 g) and Gestational Age Group (<= 28 Weeks, > 28 Weeks)\Safety Population
14.3.1.2.7	Overall TEAEs Across All Birth Weight Stratifications and by Gestational Age Group (<= 28 Weeks, > 28 Weeks)\Safety Population
14.3.1.3.1	TEAEs by System Organ Class and Preferred Term by Birth Weight Stratification (2000 - 1501 g, 1500 – 1000 g)\Safety Population
14.3.1.3.2	TEAEs by System Organ Class and Preferred Term by Birth Weight Stratification (999 - 750 g, 749 – 500 g)\Safety Population
14.3.1.3.3	TEAEs by System Organ Class and Preferred Term Across All Birth Weight Stratifications\Safety Population
14.3.1.4.1	Grade 3 TEAEs by System Organ Class and Preferred Term by Birth Weight Stratification (2000 - 1501 g, 1500 – 1000 g)\Safety Population
14.3.1.4.2	Grade 3 TEAEs by System Organ Class and Preferred Term by Birth Weight Stratification (999 - 750 g, 749 – 500 g)\Safety Population
14.3.1.4.3	Grade 3 TEAEs by System Organ Class and Preferred Term Across All Birth Weight Stratifications\Safety Population
14.3.1.5.1	Treatment Related TEAEs by System Organ Class and Preferred Term by Birth Weight Stratification (2000 - 1501 g, 1500 – 1000 g)\Safety Population
14.3.1.5.2	Treatment Related TEAEs by System Organ Class and Preferred Term by Birth Weight Stratification (999 - 750 g, 749 – 500 g)\Safety Population
14.3.1.5.3	Treatment Related TEAEs by System Organ Class and Preferred Term Across All Birth Weight Stratifications\Safety Population
14.3.1.6.1	Grade 3 Treatment Related TEAEs by System Organ Class and Preferred Term by Birth Weight Stratification (2000 - 1501 g, 1500 – 1000 g)\Safety Population

14.3.1.6.2	Grade 3 Treatment Related TEAEs by System Organ Class and Preferred Term by Birth Weight Stratification (999 - 750 g, 749 – 500 g)\Safety Population
14.3.1.6.3	Grade 3 Treatment Related TEAEs by System Organ Class and Preferred Term Across All Birth Weight Stratifications\Safety Population
14.3.2.1.1	Treatment Emergent SAEs by System Organ Class and Preferred Term and Birth Weight Stratification (2000 - 1501 g, 1500 – 1000 g)\Safety Population
14.3.2.1.2	Treatment Emergent SAEs by System Organ Class and Preferred Term by Birth Weight Stratification (999 - 750 g, 749 – 500 g)\Safety Population
14.3.2.1.3	Treatment Emergent SAEs by System Organ Class and Preferred Term Across All Birth Weight Stratifications\Safety Population
14.3.2.2.1	TEAEs Leading to Discontinuation of Study Treatment by System Organ Class and Preferred Term and Birth Weight Stratification (2000 - 1501 g, 1500 – 1000 g)\Safety Population
14.3.2.2.2	TEAEs Leading to Discontinuation of Study Treatment by System Organ Class and Preferred Term and Birth Weight Stratification (999 - 750 g, 749 – 500 g)\Safety Population
14.3.2.2.3	TEAEs Leading to Discontinuation of Study Treatment by System Organ Class and Preferred Term Across All Birth Weight Stratifications\Safety Population
14.3.2.3.1	TEAEs Leading to Death by System Organ Class and Preferred Term and Birth Weight Stratification (2000 - 1501 g, 1500 – 1000 g)\Safety Population
14.3.2.3.2	TEAEs Leading to Death by System Organ Class and Preferred Term and Birth Weight Stratification (999 - 750 g, 749 – 500 g)\Safety Population
14.3.2.3.3	TEAEs Leading to Death by System Organ Class and Preferred Term Across All Birth Weight Stratifications\Safety Population
14.3.5.1.1	Temperature (degree celsius) by Birth Weight Stratification (2000 - 1501 g, 1500 – 1000 g)\Safety Population
14.3.5.1.2	Temperature (degree celsius) by Birth Weight Stratification (999 - 750 g, 749 – 500 g)\Safety Population
14.3.5.1.3	Temperature (degree celsius) Across All Birth Weight Stratifications\Safety Population
14.3.5.2.1	Heart Rate (bpm) by Birth Weight Stratification (2000 - 1501 g, 1500 – 1000 g)\Safety Population
14.3.5.2.2	Heart Rate (bpm) by Birth Weight Stratification (999 - 750 g, 749 – 500 g)\Safety Population

14.3.5.2.3	Heart Rate (bpm) Across All Birth Weight Stratifications\Safety Population
14.3.5.3.1	Respiratory Rate (breaths/minute) by Birth Weight Stratification (2000 - 1501 g, 1500 – 1000 g)\Safety Population
14.3.5.3.2	Respiratory Rate (breaths/minute) by Birth Weight Stratification (999 - 750 g, 749 – 500 g)\Safety Population
14.3.5.3.3	Respiratory Rate (breaths/minute) Across All Birth Weight Stratifications\Safety Population
14.3.5.4.1	Systolic Blood Pressure (mmHg) by Birth Weight Stratification (2000 - 1501 g, 1500 – 1000 g)\Safety Population
14.3.5.4.2	Systolic Blood Pressure (mmHg) by Birth Weight Stratification (999 - 750 g, 749 – 500 g)\Safety Population
14.3.5.4.3	Systolic Blood Pressure (mmHg) Across All Birth Weight Stratifications\Safety Population
14.3.5.5.1	Diastolic Blood Pressure (mmHg) by Birth Weight Stratification (2000 - 1501 g, 1500 – 1000 g)\Safety Population
14.3.5.5.2	Diastolic Blood Pressure (mmHg) by Birth Weight Stratification (999 - 750 g, 749 – 500 g)\Safety Population
14.3.5.5.3	Diastolic Blood Pressure (mmHg) Across All Birth Weight Stratifications\Safety Population
14.3.5.6.1	SpO2 (%) by Birth Weight Stratification (2000 - 1501 g, 1500 – 1000 g)\Safety Population
14.3.5.6.2	SpO2 (%) by Birth Weight Stratification (999 - 750 g, 749 – 500 g)\Safety Population
14.3.5.6.3	SpO2 (%) Across All Birth Weight Stratifications\Safety Population
14.3.6.1.1	Physical Exam Findings by Birth Weight Stratification (2000 - 1501 g, 1500 – 1000 g)\Safety Population
14.3.6.1.2	Physical Exam Findings by Birth Weight Stratification (999 - 750 g, 749 – 500 g)\Safety Population
14.3.6.1.3	Physical Exam Findings Across All Birth Weight Stratifications\Safety Population
14.3.6.2.1	Growth Assessment Classification by Birth Weight Stratification (2000 - 1501 g, 1500 – 1000 g)\Safety Population

14.3.6.2.2	Growth Assessment Classification by Birth Weight Stratification (999 - 750 g, 749 – 500 g)\Safety Population
14.3.6.2.3	Growth Assessment Classification Across All Birth Weight Stratifications\Safety Population
14.3.6.3.1	Feeding Method and Content by Birth Weight Stratification (2000 - 1501 g, 1500 – 1000 g)\Safety Population
14.3.6.3.2	Feeding Method and Content by Birth Weight Stratification (999 - 750 g, 749 – 500 g)\Safety Population
14.3.6.3.3	Feeding Method and Content Across All Birth Weight Stratifications\Safety Population
14.3.6.4.1	STP206 Organisms in Fecal Samples by Birth Weight Stratification (2000 - 1501 g, 1500 – 1000 g)\Safety Population
14.3.6.4.2	STP206 Organisms in Fecal Samples by Birth Weight Stratification (999 - 750 g, 749 – 500 g)\Safety Population
14.3.6.4.3	STP206 Organisms in Fecal Samples Across All Birth Weight Stratifications\Safety Population

NUMBER	LISTING
16.2.1.1	Study Entry and Randomization
16.2.1.2	Patient Disposition at End of Treatment
16.2.1.3	Patient Disposition at End of Study
16.2.2.1	Eligibility Criteria
16.2.2.2	Protocol Deviation
16.2.3.1	Patients Included in Per Protocol Population
16.2.3.2	Patients Included in Intent-to-Treat Population
16.2.4.1.1	Maternal Demographic and Reproductive History
16.2.4.1.2	Maternal Pregnancy and Delivery History
16.2.4.1.3	Infant Demographic and Newborn Assessments
16.2.4.2	Infant Baseline Characteristics

16.2.4.3.1	Maternal Medical History
16.2.4.3.2	Infant Medical History
16.2.4.5.1	Maternal Prior and Concomitant Medications
16.2.4.5.2	Infant Prior and Concomitant Medications
16.2.4.5.3	Infant Concurrent Treatment
16.2.5	Study Drug Exposure
16.2.6.1.1	NEC Evaluation
16.2.6.1.2	NEC Treatment
16.2.6.2.1	Sepsis, Aerobic and Anaerobic Cultures Evaluations
16.2.6.2.2	Sepsis Assessment of Gram Bacilli Result
16.2.6.3.1	Feeding Volumes and Administration
16.2.6.3.2	Feeding Tolerance Evaluation
16.2.6.4	Infant Concomitant Antibiotic Usage for Underlying Infection
16.2.6.5	Other Complications of Prematurity - BPD
16.2.6.6	Other Complications of Prematurity - IVH
16.2.6.7	Other Complications of Prematurity - ROP
16.2.6.8	Other Complications of Prematurity - Spontaneous Gastrointestinal Perforation
16.2.6.9	Other Complications of Prematurity - PDA
16.2.7.1	Adverse Events\Safety Population
16.2.7.2	Serious Adverse Events\Safety Population
16.2.7.3	Listing of Adverse Event Leading to Discontinuation of Study Treatment\Safety Population
16.2.7.4	Listing of All Adverse Events with an Outcome of Death\Safety Population
16.2.7.5	Sterile Site Infection, Aerobic and Anaerobic Cultures Evaluation\Safety Population
16.2.8.2	Vital Signs at Week 1 Day 1 Dosing Period\Safety Population

16.2.8.4	Physical Examination at Pre-Dose and Week 1 Day 1 Dosing Period\Safety Population
16.2.8.5.1	Fecal Samples Evaluations\Safety Population
16.2.8.5.2	Growth Assessment\Safety Population

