
Study Endpoints:
 
Primary Endpoint:
 
 
The incidence and severity of adverse events (AEs), serious adverse events (SAEs), and changes in clinical parameters from baseline in STP206-treated subjects compared to control subjects from baseline through 30 days after the last dose of blinded study treatment
 
 
Secondary Endpoints:
 
 
The incidence and the severity of AEs and SAEs in STP206-treated subjects compared to control subjects from baseline through six months after the last dose of blinded study treatment
 
The incidence of clinical events (NEC, sepsis/bacteremia, feeding intolerance, death, morbidity/complications of prematurity) in STP206-treated subjects compared to control subjects from baseline through hospital discharge
 
The assessment of the fecal shedding of STP206 organisms in STP206-treated subjects compared to its baseline and to control subjects through the last dose of blinded study treatment
 
The assessment of the changes in routine clinical parameters in STP206-treated subjects compared to control subjects at baseline through the last dose of blinded study treatment
 
The assessment of the progression of standard neonatal growth parameters in STP206 treated subjects compared to control subjects through the 6-month postdosing visit.
 
 
Exploratory Endpoints:
 
 
The incidence of suspected NEC (Stage I NEC) in STP206-treated subjects compared to control subjects through hospital discharge
 
The incidence of suspected sepsis in STP206-treated subjects compared to control subjects through hospital discharge
 
The incidence of antibiotic usage in STP206-treated subjects compared to control subjects through hospital discharge
 

 
		
Study Design and Methodology:		

		IND No.: BB 14,046
Protocol No.: STP206-002	Development Phase: I	Indication: Necrotizing Enterocolitis
Protocol Title: A Phase Ib Randomized, Placebo Controlled Study of the Safety and Efficacy of Once Daily Dosing of STP206 in Premature Very Low Birth Weight and Extremely Low Birth Weight Neonates		

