
Study Duration:          Neonates will be dosed for between 2 and 11 weeks as determined by gestational age at birth, and all neonates will be followed until the 6-month post dosing visit. Thus, the total duration of study participation for each study subject will be between 28 and 39 weeks.
 
The total duration of the study will be approximately 55 months.
		

Study Drug, Dose, Route of Administration, and Duration of Treatment:          STP206 will be dosed orally at one of two doses
 
 
• STP 206 Low dose: approximately 1 billion (<math>1 \times 10^9</math>) cfu of [REDACTED] and approximately 100 million (<math>1 \times 10^8</math>) cfu of [REDACTED] (total of 1.1 billion cfu)
 
• STP206 High Dose: approximately 9 billion (<math>9 \times 10^9</math>) cfu of [REDACTED] and approximately 900 million (<math>9 \times 10^8</math>) cfu of [REDACTED] (total of 9.9 billion cfu)
 
 
Neonates will be dosed for between 2 and 11 weeks with the duration of dosing based upon gestational age at birth. Doses of STP206 are planned to be administered once daily, however, in neonates with dose volume restrictions, doses may be divided into a BID or TID schedule.
		

Reference Therapy, Dose Route of Administration and Duration of Treatment:          The control treatment will be dosed orally.
 
 
• Control: matching volume of water for injection United States Pharmacopeia (USP).
 
 
Neonates will be dosed for between 2 and 11 weeks with the duration of dosing based upon gestational age at birth. Doses of the control treatment are planned to be administered once daily; however, in neonates with dose volume restrictions, doses may be divided into a BID or TID schedule.
		

Criteria for Evaluation:
 
Safety Variables: Adverse events, SAEs, and changes in clinical (physical examinations, vital signs), growth parameters (head circumference, body length, body weight)
 
Efficacy Variables: Feeding intolerance, clinical events (NEC, sepsis/bacteremia, feeding intolerance, death, morbidity/complications of prematurity)
 
Pharmacokinetic Variables: None
 
Pharmacodynamic Variables: None
 
Other Variables: Fecal shedding
		

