### **6.3. Endpoints**

#### **6.3.1. Primary Endpoints**

The incidence and severity of AEs, SAEs and changes in clinical parameters in STP206-treated subjects compared to control subjects from baseline through 30 days after the last dose of blinded study treatment.

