### 12.2. Definitions

#### 12.2.1. Adverse Event

An **adverse event** (AE) is any untoward medical event associated with the use of a drug in humans, whether or not considered drug-related. An AE can therefore be any unfavorable and unintended sign (including an abnormal laboratory finding, for example), symptom, or disease temporally associated with the use of a drug and does not imply any judgment about causality.

Based upon the above definition of an AE, physical examination findings/abnormalities (inclusive of severity, nature and duration of the finding) that, in the opinion of the principal investigator, are expected to be observed in this patient population would not be considered untoward medical events and do not require reporting as AEs.

An untoward medical event which occurs outside the period of follow-up as defined in the protocol will not be considered an AE. Worsening of a medical condition for which the efficacy of the study drug is being evaluated will not be considered an AE.

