8.7.4 Other Observations Related to Safety

Growth assessments during the dosing period and post dosing period will be summarized as AGA, SGA/Head-Spared, SGA/Symmetric, LGA at the following time points: Pre-dose, Week 1 (Days 5-7), Week 2, 4, 6, 8, 10, and Post Dosing 1 Week, Post Dosing 1, 3 6 Month, and Early Withdrawal Prior to post dosing 6 Months. Four classifications (AGA, SGA/Head-Spared, SGA/Symmetric, and LGA) according to the growth chart for males and females will be summarized and displayed. Classifications will be based on weight and head growth measurements¹³ specified in Appendix D of the protocol and the WHO standard growth charts https://www.cdc.gov/growthcharts/who_charts.htm.

Information on feeding method (bottle, breast, and tube) and content of feedings (formula or breast milk), abdominal evaluation, etc will be summarized by number and percent of subjects.

Physical examination will be summarized by the number and percent of subjects with abnormal findings at the following time points: Pre-dose, and 3 hours Post Dosing.

Vital signs (BP, HR, RR, and Temperature) will be summarized as descriptive statistics (N, mean, SD, median, 25th and 75th quartiles, minimum, and maximum) and change from baseline at the following time points: Pre-dose, 1 hour, 2, 3, 4, 8, 12, 16, 20 and 24 hours post dosing.

The number and percentage of subjects with presence of STP206 organisms in fecal samples will be summarized, and the quantity (CFU) of the STP206 organisms detected from fecal shedding will be further summarized as descriptive statistics (N, mean, SD, median, 25th and 75th quartiles, maximum, and minimum) at the following time points: Pre-dose, Week 1 Days 1- 4), Week 1 (Days 5-7), Week 2, 3, 4, 5, 6, 7, 8, 9, 10, 11, End of Dosing or Hospital Discharge, whichever occurs first.

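### SAP 8.7.4 summarises physical examination as percent abnormal at two times, which does not give the number of infants newly abnormal after dosing; a shift table would

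*SAP*

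**What the plan says.** The primary endpoint has a change component. Protocol 6.3.1 reads "The incidence and severity of AEs, SAEs and changes in clinical parameters in STP206-treated subjects compared to control subjects from baseline through 30 days", with the 30 days counted from the final dose, and the synopsis words the same component as "changes in clinical parameters from baseline in STP206-treated subjects compared to control subjects". Under its criteria for evaluation, the synopsis lists the safety variables as including "changes in clinical (physical examinations, vital signs), growth parameters". Physical examination is therefore one of the parameters whose change is to be assessed.

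SAP 8.7.4 treats the two clinical parameters differently in adjacent paragraphs. Physical examination is "summarized by the number and percent of subjects with abnormal findings at the following time points: Pre-dose, and 3 hours Post Dosing". Vital signs get descriptive statistics and "change from baseline at the following time points: Pre-dose, 1 hour, 2, 3, 4, 8, 12" and onward to 24 hours. No shift, new-onset count or other within-infant measure is stated for the examination.

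The output is Tables 14.3.6.1.1 and 14.3.6.1.2 ("Physical Exam Findings by Birth Weight Stratification") and 14.3.6.1.3 across all strata. These titles show neither statistic nor time point, and SAP section 11 says that the shells are in a separate document. The evidence is therefore the text of 8.7.4. SAP 5.2 declares one change from the protocol's analyses, the ITT definition, so the examination summary is not presented as a departure.

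**The concern.** An endpoint defined as change from baseline needs each infant's two examinations to be compared. The percent abnormal at each of two times describes the group twice and does not link the infants. Two things can then go unseen.

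- **Offsetting.** One infant's new abnormality and another's resolved abnormality leave the percentage unchanged.
- **Masking by another body system.** Protocol 10.3.1 examines eight systems, but SAP 8.7.4 counts subjects with abnormal findings and does not say that the count is per system. If it is per infant, an infant with a pre-dose respiratory finding and a new abdominal finding is abnormal at both times. The new finding then disappears without any resolution.

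This is a safety-primary study with cohorts of 8 STP206 and 4 control infants, and Protocol 7.7 and SAP 7.4.2 put available primary endpoint data before the DSMC at each review. In groups this small, one or two new findings after dosing are worth counting, and the stated summary does not count them.

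**Working it through.** The plan gives no figure for this point, so there is nothing to reproduce. The check is what the planned summary can and cannot reveal.

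**Inputs**
- Infants per cohort: 12, randomised 2:1 (Protocol 7.1). STP206: 12 × 2/3 = 8. Control: 12 × 1/3 = 4.
- Pooled STP206 infants per dose over four strata: 8 × 4 = 32.
- Rates of abnormal, new or resolved findings: not given in the documents. The values below are assumptions.

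**Bounds for one body system**

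Of n infants, let a be abnormal pre-dose and b at 3 hours. Let x go from normal to abnormal and y from abnormal to normal. Then b = a + x − y. Since x cannot exceed n − a or b, and y cannot be negative:

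max(0, b − a) ≤ x ≤ min(b, n − a)

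| n | a | b | Planned table shows | Newly abnormal, x |
|---|---|---|---|---|
| 8 | 2 | 2 | 25%, 25% | 0 to 2 |
| 8 | 4 | 4 | 50%, 50% | 0 to 4 |
| 32 | 8 | 8 | 25%, 25% | 0 to 8 |
| 32 | 16 | 16 | 50%, 50% | 0 to 16 |

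If a = 0, both bounds equal b and nothing is lost. The ambiguity exists only where some infants are abnormal before dosing.

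**If the count is per infant over all systems**

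Let z be the infants with a new finding in at least one system. Any such infant is abnormal at 3 hours, so z can be as large as b, whatever n − a is. With n = 8 and a = b = 6, x is limited to min(6, 8 − 6) = 2, but z can be 6. With a = b = 4, z can reach 4 with no finding resolving.

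**How often offsetting could matter (assumed rates)**

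Take one system, n = 8, a = 4, independent infants, onset probability p in each of the 4 normal infants and resolution probability r in each of the 4 abnormal ones.

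- P(at least one new) = 1 − (1 − p)^4
- P(at least one new, and percent abnormal does not rise) = Σ over k = 1 to 4 of P(x = k) × P(y ≥ k)

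For p = r = 0.1 the first is 1 − 0.9^4 = 0.344. The second is 0.2916 × 0.3439 + 0.0486 × 0.0523 + smaller terms = 0.103.

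| p | r | At least one new | New, but no rise | Share unseen |
|---|---|---|---|---|
| 0.1 | 0.1 | 0.344 | 0.103 | 30% |
| 0.2 | 0.2 | 0.590 | 0.270 | 46% |
| 0.3 | 0.3 | 0.760 | 0.411 | 54% |
| 0.2 | 0 | 0.590 | 0 | 0% |

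Offsetting can be common if findings resolve as often as they arise, and is absent if none resolve.

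**The case against.** The strongest case against has four parts.

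- **Randomised control.** Safety data are shown for control as well (SAP 8.7). If resolution is similar in the arms, onset caused by treatment still appears as a higher 3-hour percentage than in control. This stands: what is shown is ambiguity within an arm, and a reader who infers that the between-arm comparison is lost goes too far. But 8 against 4 gives no assurance that pre-dose findings balance, and masking by another system dulls the comparison in both arms.
- **Other outputs.** New or worsened examination findings are to be captured as events (Protocol 12.3) and tabulated as treatment-emergent (SAP 8.7.2). Abdominal evaluation, feeding intolerance, NEC, respiratory rate and SpO2 have their own summaries. Listing 16.2.8.4 sets out each infant's pre-dose and Day 1 examinations. Most of this stands. The remaining gap is that findings which, in the principal investigator's opinion, "are expected to be observed in this patient population would not be considered untoward medical events and do not require reporting as AEs" (Protocol 12.2.1) can stay out of the event tables, although that exemption takes severity, nature and duration into account. A listing is not a comparison between arms.
- **Short interval.** Offsetting needs a finding to resolve between the pre-dose examination and 3 hours (±1 hour) after the first dose, and the documents give no reason to expect this often. This stands as a limit on offsetting, but not on masking by another system.
- **Shells not seen.** A shift layout there cannot be excluded. True, but SAP 8.7.4 states the analysis, and it states two percentages.

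**Conclusion.** The point holds, with modest consequence. For physical examination, a named part of the primary endpoint, SAP 8.7.4 states no within-infant change, and its two percentages leave the newly abnormal count open: 0 to 4 with 4 of 8 abnormal at both times, 0 to 16 with 16 of 32.

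Two stronger readings are tempting and not supported. One is that new abnormalities are cancelled by resolved ones. They can be; the assumed rates above put the unseen share anywhere from 0% to 54%, and the documents give no rates. The other is that the change-from-baseline endpoint is not computed. Vital signs do have change from baseline, and treatment-emergent events are themselves defined by onset or worsening after the first dose. Only the examination component lacks a change measure.

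The size rests on some infants being abnormal before dosing, which is plausible in this population but not quantified in the documents. All comparisons are exploratory (SAP 7.1), so no formal inference is affected. That the examination summary stops 3 hours after the first dose, while the endpoint runs to 30 days after the last, is a separate matter.

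**What to change.** In SAP 8.7.4 and Tables 14.3.6.1.1 to 14.3.6.1.3, add a shift table for each of the eight body systems in Protocol 10.3.1: pre-dose normal or abnormal by 3-hour normal or abnormal, for each arm. Report the number and percent of infants normal pre-dose and abnormal at 3 hours, and state the denominator. Use the SAP 6.2.2 rule for baseline (last assessment before the first dose). The planned percentages remain as the margins of the shift table, so nothing is lost.

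The cost is a change of table layout. Protocol 10.3.1 puts the screening and Day 1 examinations on the CRF, Protocol 11.3.2.1 schedules examinations before dosing and at 3 hours, and Listing 16.2.8.4 already draws on them. This assumes that the CRF records findings by body system, which should be confirmed. If the shells already contain such a layout, SAP 8.7.4 need only say so.
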